3.5.3. Average EAIR on a global level

The average *EAIR* on a global level only considers the first event per patient across all events. The denominator includes the exposure times of all PTs, i.e.

$$EAIR_{global} = \sum_{i=1}^{n} TEAE_{i} \sum_{PT=1}^{n} \frac{1}{t_{PT,i}},$$

where $TEAE_i$ is the first event of a patient overall and the $t_{PT,i}$'s are PT-specific exposure times of that patient.

Note: This EAIR is an incidence rate per average (or typical) preferred term.

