3. EXPOSURE ADJUSTED INCIDENCE RATES (EAIR)

3.1. Restriction on the first event

The analysis restricts on the occurrence of the first event per patient and ignores the existence of later (multiple) events as these cannot be assumed to occur independent of previous events (e.g.: patients suffering from infections may have in general a higher risk of having other complications and may even have a higher risk of getting other infections). The occurrence of multiple events is subject to another analysis considering the absolute number of adverse events per patient.

For these reasons the EAIR should be interpreted as 'rate until the first event occurs'. Rates estimated from several patients can be averaged on the level of a preferred term (PT), of a system organ class (SOC), or on a global level (see below).

The interpretation of EAIRs is simple and consistent on the preferred-term level only, and can be expressed as "Average number of TEAEs per preferred-term emerging per person-month of exposure".

The aforementioned considerations apply in the same way to EAIRs estimated on the global level: when EAIRs are collapsed into the global estimate (first analyses), the estimate can be interpreted as the "Average number of TEAEs emerging per person-month and PT", because estimation has been performed on a 'per PT'-basis (per average or typical PT among all PTs).

Comparing EAIRs on the level of the SOC or on the global level involves data destruction because a patient's information is reduced to the first TEAE only (and possibly to a TEAE of marginal relevance among many TEAEs with higher clinical relevance).

The EAIR analysis focuses on the 'speed' by which TEAEs emerge. The analysis restricts on the first event of a patient because independence of TEAEs cannot be assumed. The necessity to restrict on the first event entails considerable data destruction when deriving SOC-specific EAIRs or the EAIR on a global level. To overcome this, the 'per PT'-analysis, which is reported in both Tables identically, is preferable.

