Comparing EAIRs between the analyses outlined below on a SOC-specific or a global level demonstrates that the 'per PT'- method makes the interpretation of results more difficult. However, it can be suggested that this method provides a more robust approach when the two treatment arms are to be compared on a SOC-specific or global level. A t-Test like comparison of PT-specific estimates between the two treatment arms may provide a more robust, comprehensive and easy-to-communicate way of visualizing and comparing results.

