3.5.2. Average EAIR per SOC

The average *EAIR* per SOC considers the first event of each patient within the SOC. The denominator includes the exposure time of each adverse event of all PTs within the SOC, per patient, i.e.

$$EAIR_{SOC} = \sum_{i=1}^{n} TEAE_{SOC,i} \sum_{PT=1}^{n \ PTs \ per \ SOC} \frac{1}{t_{PTi}}$$

where $TEAE_{SOC,i}$ is the first event per patient per SOC and $t_{PT,i}$ is the exposure time for a specific preferred term of a given patient.

Note: This *EAIR* is an incidence rate per *average* (or typical) preferred term in that SOC (cf. 3.6.1).

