3.6.2. Average EAIR per SOC

The average EAIR per SOC considers the first event per patient per SOC only, and only one (the corresponding) exposure time in the denominator (confer before, where the denominator in the $EAIR_{SOC}$ depends on the number of PTs per SOC):

$$EAIR_{SOC} = \frac{\sum_{i=1}^{n} TEAE_{SOC,i}}{\sum_{i=1}^{n} t_{SOC,i}},$$

Note: This EAIR is an incidence rate per SOC.

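### The SOC-level and global per-PT adverse-event rates in SAP Attachment 1 (3.5.2, 3.5.3) divide one event per patient by the exposure of every preferred term, so for common events these two exploratory summaries mostly track treatment duration.

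*SAP*

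**What the plan says.** Attachment 1 of the SAP holds additional exploratory analyses to support HEMAR. Its section 3 sets out the EAIRs.

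- Section 3.2: a PT that occurs contributes time up to its first event. A PT that does not occur contributes the patient's whole treatment duration.
- Section 3.5.2: the rate "per SOC considers the first event of each patient within the SOC". On exposure it says: "The denominator includes the exposure time of each adverse event of all PTs within the SOC, per patient".
- Section 3.5.3: the corresponding rate "on a global level only considers the first event per patient across all events. The denominator includes the exposure times of all PTs".
- The notes under both describe the result as an incidence rate for an average or typical PT. Section 3.1 reads the global figure the same way, as a mean count of events for each person-month and PT; that passage opens with "when EAIRs are collapsed into the global estimate (first analyses), the estimate can be interpreted as the".
- Section 3.6.2 gives a second version that "considers the first event per patient per SOC only, and only one (the corresponding) exposure time in the denominator". It contrasts this with the 3.5 denominator, which it says "depends on the number of PTs per SOC". Section 3.6.3 does the same globally.
- Section 3.1 concedes that restricting to first events destroys data at SOC and global level and calls the PT-level analysis preferable. It also says that the per-PT method is harder to interpret, then offers the suggestion that "this method provides a more robust approach when the two treatment arms are to be compared on a SOC-specific or global level".

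**The concern.** A patient adds at most 1 to the numerator in 3.5.2 and 3.5.3 but adds exposure once for every PT to the denominator. Once nearly everyone has had some event, the numerator is fixed at about the number of patients. The denominator is then close to patients × PTs × time on treatment. The statistic responds to how long patients are treated and hardly at all to how often events occur.

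Both arms treat until progression or unacceptable toxicity, and the design assumes a hazard ratio of 0.75 for PFS. DRd exposure is therefore expected to be longer, which pushes the DRd/Rd ratio below 1 when event rates are equal and offsets a real excess.

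SAP 5.3.2 also allows an exposure-adjusted rate for infections and infestations, which is a whole SOC, without saying which formula applies. Attachment 1 is where the SAP defines such rates.

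**Working it through.** The SAP states no EAIR value, so there is no figure to reproduce.

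**Inputs from the documents.** 365 patients per arm; median PFS on Rd 24 months; hazard ratio 0.75, so a DRd median of 24/0.75 = 32 months; 21 months of accrual plus 24 months, so follow-up of 24 to 45 months; treatment to progression. With exponential treatment times, mean exposure is about 21.7 months (Rd) and 24.1 months (DRd).

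**Assumed, because the documents do not give them.** Number of PTs, adverse-event rates, constant hazards, and a doubling that applies to every PT.

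**Closed form.** Take K PTs, each with hazard λ, and a fixed treatment time D.

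- Numerator per patient: 1 − exp(−KλD).
- Denominator per patient: K(1 − exp(−λD))/λ.
- Statistic: λ(1 − exp(−KλD)) / [K(1 − exp(−λD))].

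When KλD is large and λD small, this tends to 1/(KD), and λ drops out. When KλD is small it tends to λ, the true rate.

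**Global example.** K = 400 and 2 events per patient-month on Rd, so λ = 2/400 = 0.005.

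- Rd, D = 21.7: 0.005/(400 × 0.1028) = 0.0001216, about 2% of the true 0.005.
- DRd, equal rate, D = 24.1: 0.005/(400 × 0.1135) = 0.0001101. Ratio 0.91, against an inverse exposure ratio of 21.7/24.1 = 0.90.
- DRd, doubled rate, λ = 0.010: 0.010/(400 × 0.2142) = 0.0001167. Ratio 0.96.

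**Simulation with variable treatment times**, DRd/Rd ratio from 3.5.2/3.5.3 as the text describes them:

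| Setting (share of Rd patients with an event) | Equal rates | True doubling |
|---|---|---|
| Global, 400 PTs (98–99%) | 0.91 | 0.95–0.96 |
| SOC, 40 PTs, 0.30/month (91%) | 0.91 | 1.03 |
| SOC, 40 PTs, 0.15/month (83–84%) | 0.93–0.94 | 1.05 |
| SOC, 20 PTs, 0.10/month (76–77%) | 0.95 | 1.13–1.15 |
| SOC, 20 PTs, 0.03/month (44%) | 0.99 | 1.40–1.46 |
| SOC, 10 PTs, 0.005/month (10%) | 0.98 | 1.80–1.92 |

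Under a doubling, the 3.6.2/3.6.3 rates give about 1.9 to 2.06. The mean of the PT-level EAIRs gives about 2.0 (1.92 to 2.06). Both give about 1.0 when rates are equal.

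**Sensitivity.**

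- With equal treatment durations in the two arms, a doubling still shows globally as only 1.04 to 1.06. The masking does not depend on DRd being given longer.
- With 100 to 500 PTs and no administrative cut-off, equal rates can give as little as 0.79 globally, and a doubling shows as 0.91 to 1.07.
- With 0.5% per month extra discontinuation on DRd (assumed), mean exposure is about 21.7 and 22.4 months and the ratio at equal rates rises to 0.97–0.98.
- Read exactly as printed, as a sum of 1/t, a doubling shows as about 1.1 globally and 1.4 to 1.7 by SOC. That quantity is not divided by the number of patients and is dominated by very early events.
- If only PTs that occurred enter the denominator, a doubling shows as 0.41 to 0.58 globally, which reverses its direction.

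**The case against.** The strongest reply is that nothing important rests on these two summaries. They are exploratory. The main safety section of the SAP does not use the 3.5 formulas. Attachment 1 also plans PT-level EAIRs (3.5.1, 3.6.1), matched first-event rates (3.6.2, 3.6.3), and hazard ratios with Kaplan-Meier curves for any, serious, fatal, Grade 3 or 4 and other event classes (section 4). This stands. A reader might infer that the plan as a whole could miss a doubling of toxicity, and the documents do not support that.

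Second, the sentence in 3.1 is hedged. It follows an admission that the method is harder to interpret, and the next sentence proposes comparing PT-specific estimates, which are sound. It may mean those rather than the 3.5.2/3.5.3 aggregates. This stands in part: it is too much to say that the SAP adopts the aggregates as its method for comparing arms. But the sentence speaks of SOC and global comparisons, and at those levels 3.5.2 and 3.5.3 are what the per-PT heading defines.

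Third, the estimator is not settled. The printed formulas are sums of 1/t, which may be a fraction lost in reading the PDF, and the notes would also fit a mean of PT-level EAIRs, which is correct. The ambiguity is real, but the prose in 3.5.2 and 3.5.3 and the contrast drawn in 3.6.2 both describe a denominator summed over PTs. Text, formula and note disagree and need to be reconciled in any case.

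Fourth, stopping for toxicity could narrow the exposure gap. It does, and the sensitivity run shows less bias at equal rates. The insensitivity to a true excess remains.

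**Conclusion.** The concern holds for the SOC and global per-PT rates as their text defines them. Globally, and in SOCs affecting most patients (about 83% or more in these settings), equal rates give a ratio of about 0.90 to 0.97 and a true doubling shows as about 0.95 to 1.12. These ranges cover stopping for progression only and some extra discontinuation on DRd. They rest on assumed event rates, PT counts and a uniform doubling. The mismatch itself is algebra and does not depend on those assumptions.

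Two further inferences should be resisted. One is that the statistic can never tell no added toxicity from twice the toxicity. That fails in less common SOCs, where a doubling shows as about 1.4 to 1.5 at 44% affected and as most of its true size when about 10% are affected. The other is to attach false-significance rates to it: the SAP specifies no test on the 3.5.2 or 3.5.3 figures. The point merits correction but touches no efficacy result, stopping rule or main safety table.

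**What to change.** 1. In 3.5.2 and 3.5.3, define the rate as the mean of the PT-level EAIRs from 3.5.1, over the PTs in the SOC or over all PTs. This matches the SAP's own notes and recovers a doubling as about 2.0. Use the same PT list in both arms, so that a PT with no event in one arm enters as zero. Pooling PT-level events over PT-level exposure also matches numerator to denominator, but it shrinks a doubling to about 1.75 to 1.9 when PT frequencies are uneven.
2. State that arms are compared at SOC and global level with 3.6.2 and 3.6.3.
3. Delete or reword the sentence in 3.1 that calls the per-PT method more robust for that comparison.
4. If the optional infection rate in SAP 5.3.2 is produced, name the formula it uses.

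The cost is two formulas, a few sentences and minor reprogramming, with no new data. The SOC and global figures for DRd may look less favourable than under the present definitions.

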3.6. Second analyses

3.6.1. Average EAIR per PT

The EAIR for a specific PT is an average over all patients as described before, i.e.

$$EAIR_{PT} = \frac{\sum_{i=1}^{n} TEAE_{PT,i}}{\sum_{i=1}^{n} t_{PT,i}},$$

whereby the number of TEAEs and durations of exposure enter the nominator and the denominator

3.6.2. Average EAIR per SOC

The average EAIR per SOC considers the first event per patient per SOC only, and only one (the corresponding) exposure time in the denominator (confer before, where the denominator in the $EAIR_{SOC}$ depends on the number of PTs per SOC):

$$EAIR_{SOC} = \frac{\sum_{i=1}^{n} TEAE_{SOC,i}}{\sum_{i=1}^{n} t_{SOC,i}},$$

Note: This EAIR is an incidence rate per SOC.

3.6.3. Average EAIR on a global level

The average EAIR on a global level considers the overall first event per patient only, and only one (the corresponding) exposure time in the denominator (confer before, where the denominator in the $EAIR_{SOC}$ depends on the overall number of PTs):

$$EAIR_{global} = \frac{\sum_{i=1}^{n} TEAE_{i}}{\sum_{i=1}^{n} t_{i}}$$
,

whereby $TEAE_i$ represents the first TEAE among all TEAEs of patient i and t_i as before (time when TEAE occurs (non-censored data) or total duration of treatment if no event occurs (censored data))

4. ADDITIONAL TIME TO EVENT ANALYSES

In case of different exposure times, time adjustment for AE is necessary. Hazard Ratio and Kaplan-Meier curves will be conducted including number of patients at risk for the following safety endpoints:

- Any TEAE
- Any Serious TEAE
- Any TEAE leading to death
- Any Grade 3 or 4 TEAE
- Any Grade 3 or higher TEAE
- Any TEAE leading to treatment discontinuation

Detailed description by preferred term:

- TEAEs by preferred term with prevalence>=10%/
- Grade 3 or 4 TEAEs preferred term with prevalence>=5%
- Grade 3 or higher TEAEs by preferred term prevalence>=5%
- Serious TEAEs preferred term with prevalence>=2%
- TEAEs leading to treatment discontinuation preferred term with prevalence>=1%
- TEAE leading to death preferred term without prevalence cut-off

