Subject participation will include a Screening Phase, a Treatment Phase, and a Follow-up Phase. The Screening Phase will be up to 21 days before Cycle 1 Day 1. The Treatment Phase will extend from Day 1 of Cycle 1 until discontinuation of all study treatment. For subjects assigned to DRd, daratumumab will be administered weekly for the first 8 weeks (Cycles 1-2) of treatment and then every other week for 16 weeks (Cycles 3-6), then every 4 weeks (from Cycle 7 and beyond) until disease progression or unacceptable toxicity. This will equate to 9 consecutive weeks of dosing at the start of the study and a total of 23 doses in the first year. Lenalidomide will be administered at a 25 mg or 10 mg orally (PO) on Days 1 through 21 of each 28-day cycle, and dexamethasone will be administered at a dose of 40 mg or 20 mg once a week for both treatment arms (per age, for more detail refer to protocol Section 6. Dosage and Administration). Those in the Rd arm will receive lenalidomide will be administered at a dose of 25 mg or 10 mg orally (PO) on Days 1 through 21 of each 28-day cycle, and dexamethasone will be administered at a dose of 40 mg or 20 mg once a week until disease progression or unacceptable toxicity. Subjects in both treatment arms will continue lenalidomide and dexamethasone until disease progression or unacceptable toxicity. In the DRd arm, subjects will continue on daratumumab until disease progression or unacceptable toxicity.

The Follow-up Phase will begin once a subject discontinues all study treatments. Subjects who discontinue for reasons other than disease progression must continue to have disease evaluations according to the Time and Events Schedule which will continue until confirmed progression disease (PD), death, lost to follow up, consent withdrawal, subsequent anticancer therapy, or

study end, whichever occurs first. After the clinical cut-off (see below for definition), data collection will be reduced as per protocol Section 9.1.4.

Two interim analyses are planned (for detail refer to Section 1.4).

The primary PFS analysis will occur when approximately 390 PFS events have been observed. The date established for the primary PFS analysis will serve as the clinical cut-off date, after which data collection in the study will be reduced. Investigators will be informed when each interim analysis is to occur. All available data prior to that time will be included in each of the respective analyses.

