2.8. General Analysis Method

In general, continuous variables will be summarized using descriptive statistics such as mean, standard deviation (SD), median and range. Categorical variables will be summarized using frequency and percentage. For time-to-event variables, which is defined as from randomization to the date of the event, the Kaplan-Meier method will be used for descriptive summaries. For the calculation of time-to-event and duration-of-event variables, the difference between the start date and the end date plus 1 day will be used.

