5.1. Adverse Events

All adverse events whether serious or non-serious, will be reported from the time a signed and dated informed consent form (ICF) is obtained until 30 days after the last dose of study treatment, until the subject withdraws consent for study participation, or until the subject starts subsequent antimyeloma therapy, whichever occurs first. AEs will be recorded in standard medical terminology and graded according to the National Cancer Institute Common Terminology Criteria for Adverse Events (NCI-CTCAE), Version 4.03. For AE reporting, the verbatim term used in the CRF by investigators to identify adverse events will be coded using the latest version of Medical Dictionary for Regulatory Activities (MedDRA) coding dictionary.

Unless otherwise specified, at each level (e.g., system organ class and/or preferred term) of subject summarization in reporting the incidence of the AE, a subject is counted once if one or more events were recorded. For summarizing new onset events, all event records of the same preferred term from the same subject are to be linked by the onset date and the end date. If an event is followed by another event of the same preferred term with an onset date (or date/time) the same as or 1 day (or 1 minute if applicable) after the end date (or date/time) of the previous record and any features of the adverse event (i.e.: toxicity grades/seriousness/action taken) are different between these two records, these 2 records should be linked together and considered as one event. A Grade 5 event will be linked to previous event of the same preferred term if the onset date of grade 5 record is the same or one day after the end date of previous record.

All summaries of AEs will be based on treatment-emergent adverse events (TEAEs), which are defined as any AE that occurs after start of the first study treatment through 30 days after the last study treatment; or the day prior to start of subsequent antimyeloma therapy, whichever is earlier; or any AE that is considered drug-related (very likely, probably, or possibly related) regardless of the start date of the event; or any AE that is present at baseline but worsens in toxicity grade or is subsequently considered drug-related by the investigator.

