3.2. Duration of exposure: censored & non-censored

The incidence rate for a patient is derived from the duration of exposure to treatment of that patient. When averaging incidence rates, a patient's duration of exposure is given either A) by the time when the event has occurred (non-censored data), or B) by the total duration of treatment in case the patient does not show the adverse event in question (censored data). Depending on whether a patient has an adverse event or not, the duration of exposure enters the denominator in its non-censored or censored form, respectively.

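### Kaplan-Meier curves for TEAE endpoints in SAP Attachment 1 have no competing-risk counterpart, so one minus Kaplan-Meier will overstate the proportion of subjects affected

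*SAP*

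**What the plan says.** SAP Attachment 1, which holds exploratory analyses for HEMAR, plans time-to-event analyses of TEAEs in its section 4. The stated reason is that "In case of different exposure times, time adjustment for AE is necessary". The method is that "Hazard Ratio and Kaplan-Meier curves will be conducted including number of patients at risk for the following safety endpoints", and the list includes "Any TEAE leading to treatment discontinuation". Section 4 does not say when a subject without the event is censored. SAP section 2.8 is no more specific: for time-to-event variables, "the Kaplan-Meier method will be used for descriptive summaries". Neither document mentions cumulative incidence functions or competing risks.

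Three other places fix how subjects leave the risk set:

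- SAP section 1.1: "Subjects in both treatment arms will continue lenalidomide and dexamethasone until disease progression or unacceptable toxicity". Daratumumab follows the same rule in the DRd arm.
- SAP section 5.1: a TEAE is "any AE that occurs after start of the first study treatment through 30 days after the last study treatment". The window closes sooner if a new myeloma treatment begins. AEs judged drug-related count whatever their start date.
- SAP Attachment 1 section 3.2, written for the exposure-adjusted incidence rates: an event-free subject's exposure is given "by the total duration of treatment in case the patient does not show the adverse event in question (censored data".

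**The concern.** A subject who has stopped all treatment for progression, or has died, cannot later stop treatment because of a TEAE. In a treat-to-progression trial, these exits are likely to be a major route out of the risk set. If they enter a Kaplan-Meier curve as censoring, one minus the curve estimates how often the event would occur if nobody progressed or died of something else. Readers of a safety or health-economic report usually take such a curve as the proportion of subjects affected, and that proportion is lower. The arms are also assumed to progress at different rates, so the overstatement need not be the same in both.

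**Working it through.** **How exits are handled.** Section 4 is silent, so this step is an inference. Treatment ends at progression (SAP 1.1). The TEAE window then closes within 30 days, or earlier if subsequent therapy starts (SAP 5.1). The attachment's only exposure rule censors event-free subjects at total treatment duration (3.2). With Kaplan-Meier as the only named method, progression and death without the event can only appear as censoring.

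**Inputs from the documents** (protocol 11.2, SAP 1.3): median PFS on Rd 24 months, hazard ratio 0.75, 390 PFS events, 80% power, two-sided alpha 0.05, about 365 subjects per arm, 21 months of accrual plus 24 of follow-up, 5% annual dropout.

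**Input that is assumed:** the TEAE hazard. Neither document gives one. I take it as constant, at 0.003 to 0.010 per month.

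**Reproducing the plan.** Schoenfeld events = 4 × (1.960 + 0.842)² / (ln 0.75)² = 380, and 390 events give 81.1% power. Exponential PFS with the stated accrual, follow-up and dropout needs about 724 subjects for 390 events, against 730 stated. The plan's PFS assumptions reproduce, so they can serve as the competing hazard.

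**Formulas.** With TEAE hazard a and hazard c of treatment ending through progression or death:

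- One minus Kaplan-Meier = 1 − exp(−a t)
- Cumulative incidence = a/(a + c) × [1 − exp(−(a + c) t)]
- c = ln 2/24 = 0.02888 per month (Rd); 0.75 × 0.02888 = 0.02166 (DRd)

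**Worked case, a = 0.006 in both arms, t = 36:**

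- One minus Kaplan-Meier: 1 − exp(−0.216) = 19.4% in both arms.
- Rd: 0.006/0.03488 × [1 − exp(−1.256)] = 0.1720 × 0.7151 = 12.3%.
- DRd: 0.006/0.02766 × [1 − exp(−0.996)] = 0.2169 × 0.6306 = 13.7%.

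**Range at 36 months, equal hazards** (errors in points, taken before rounding):

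| a per month | 1−KM, both arms | Incidence Rd | Incidence DRd | Error Rd | Error DRd | Ratio Rd | Ratio DRd |
|---|---|---|---|---|---|---|---|
| 0.003 | 10.2% | 6.4% | 7.2% | 3.8 | 3.1 | 1.59 | 1.43 |
| 0.006 | 19.4% | 12.3% | 13.7% | 7.1 | 5.7 | 1.58 | 1.42 |
| 0.010 | 30.2% | 19.4% | 21.5% | 10.9 | 8.8 | 1.56 | 1.41 |

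At 24 months with a = 0.006 the errors are 3.7 and 2.9 points.

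**Unequal hazards** (Rd fixed at 0.006, 36 months; Rd error 7.1 points, ratio 1.58):

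| DRd/Rd TEAE hazard | Error DRd | Ratio DRd | Risk ratio from KM | Risk ratio from incidence |
|---|---|---|---|---|
| 1.0 | 5.7 | 1.42 | 1.00 | 1.11 |
| 1.5 | 8.1 | 1.41 | 1.42 | 1.59 |
| 2.0 | 10.0 | 1.40 | 1.81 | 2.04 |

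The absolute errors are equal when the DRd hazard is 1.29 times that of Rd (1.26 to 1.34 over a = 0.003 to 0.010). For more frequent events the crossing comes later: 1.54 at 36 months when 20% of Rd subjects have the event by month 12.

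**Between-arm difference.** Its distortion is the difference of the two errors. At equal hazards this is 7.1 − 5.7 = 1.4 points. Greenwood standard errors at 36 months, using the plan's accrual, follow-up and dropout, are about 3.3 (Rd) and 3.0 (DRd). The standard error of the difference is √(3.3² + 3.0²), about 4.4 points, so the distortion is about 0.3 standard errors. At a hazard ratio of 2 it is 10.0 − 7.1 = 2.9 points, in the opposite direction.

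**Any TEAE.** As t grows, the error tends to c/(a + c). If 50% of subjects have a TEAE in month 1 and that hazard (0.693) continues, the limit is 0.02888/0.722 = 4.0 points in Rd and 3.0 in DRd. If 80% do, it is 1.8 and 1.3. The month-1 shares are assumptions.

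**The case against.** The strongest reply is that section 4 sets out to adjust for exposure, and Kaplan-Meier does so. With equal hazards it shows equal on-treatment toxicity. Cumulative incidence makes Rd look safer only because Rd subjects progress sooner. The crude proportions are already planned: reasons for stopping treatment in SAP 3.2, and TEAE, Grade 3 or 4, serious and discontinuation tables in 5.1.2 to 5.1.8. This stands as an argument against removing the Kaplan-Meier curves. It does not make them readable as risks, and crude tables give no risk by a stated time under unequal follow-up.

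A reader might also infer more than the documents support:

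- That the SAP states that progression is censored in these curves. It does not; the rule in section 3.2 is written for the incidence rates.
- That the overstatement is always worse in Rd, so the curves flatter DRd. The relative overstatement was larger in Rd in every scenario run. The absolute one reverses once the DRd hazard exceeds about 1.3 times that of Rd, which is plausible when a third drug is added to the same backbone.
- That every endpoint is affected alike. The error is small for any TEAE. For a TEAE leading to death, such deaths are the event, and only progression and other deaths compete.
- That the hazard ratio is wrong. It remains interpretable as a cause-specific hazard ratio.

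**Conclusion.** The point holds as a limit on how the curves can be read. One minus Kaplan-Meier will overstate the proportion of subjects with the event, by 3.1 to 10.9 points at 36 months for assumed hazards of 0.003 to 0.010 per month. That is about 1.4 to 1.6 times the cumulative incidence. The effect on the comparison of arms is much smaller, about 1.4 points at equal hazards of 0.006, and its direction depends on the unknown TEAE hazards.

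These sizes rest on constant hazards, on the planned PFS hazard standing in for treatment ending through progression or death, and on ignoring the 30-day tail and other reasons for stopping. The analysis is exploratory. PFS, alpha control and the main safety tables in SAP section 5 are not affected.

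**What to change.** In SAP Attachment 1 section 4:

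1. State the censoring rule for each endpoint.
2. Add Aalen-Johansen cumulative incidence curves by arm. Treat progression-related or other end of treatment, and death without the event, as competing events. Use these curves for any statement of risk.
3. Label the Cox hazard ratio cause-specific.
4. If the Kaplan-Meier curves are kept, label them as on-treatment, exposure-adjusted displays and not as incidence.

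The cost is a little programming and extra output. Reasons for stopping treatment and causes of death are already collected (SAP 3.2 and 5.2.2), so no new data are needed.
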